TDF	Tenofovir Disoproxil Fumarate
TEAE	Treatment Emergent Adverse Event
TFL	Tables, Figures and Listings
TND	Target not detected
VAS	Visual Analog Scale
VCTE	Vibration Controlled Transient Elastography
WHO-DD	World Health Organization Drug Dictionary

1. INTRODUCTION

The following Statistical Analysis Plan (SAP) provides the outline for the statistical analysis of the data collected from the EYP001-201 study (protocol version 3.0 dated 22 January 2020).

The planned analyses identified in this SAP may be included in clinical study reports (CSRs), regulatory submissions, or future manuscripts. Also, post hoc exploratory analyses not necessarily identified in this SAP may be performed to further examine study data. Any post hoc, or unplanned, exploratory analyses performed will be clearly identified as such in the final CSR.

2. PROJECT OVERVIEW

2.1 Study Design

This is a prospective, multi-centre, international randomized, double-blind, placebo controlled, Phase 2a experimental study of oral FXR modulator EYP001a/placebo combined with Nucleos(t)ide analogues (NA) in virologically suppressed CHB patients to improve functional cure rates.

In total 49 eligible patients will be enrolled and randomized at approximately 14 study sites in 4 countries. Patients will be randomized prior to study drug (EYP001a or placebo and NA) administration on Day 1 in the ratio of 3:1 into 2 arms:

[figure not shown]
- Experimental Arm: EYP001a 200 mg once daily (QD) + NA daily (37 patients)
- Control Arm: Placebo + NA daily (12 patients)

Patients will also be stratified per HBeAg status, based on medical history HBeAg value or established during screening, to obtain a balanced randomization to both study arms.

The maximum total engagement duration for eligible patients in this study is up to 370 days: 90 days screening, 112 days (16 weeks) experimental treatment period and 168 days (24 weeks) follow-up on NA standard of care therapy (SOC) only.

Patients enrolled in the study will be assessed as outpatients. Patient screening will occur no more than 90 days prior to the Day 1 visit. Eligible patients will undergo further assessments on Day 1 to qualify for study drug administration on Day 1.

Figure 1: Study Design

2.2 Objectives

2.2.1 Primary objective

The primary objective of this study is:

- To determine the effect of EYP001a on top of NA (standard of care (SOC) therapy) on Hepatitis B Surface Antigen (HBsAg) plasma levels.

2.2.2 Secondary objective(s)

The secondary objectives of this study are:

- To establish the effect of EYP001a on top of NA on HBsAg responder rate at the end of the 16-week EYP001a treatment and at 24-week of follow-up (Week 40).
- To establish the effect of EYP001a on top of NA on HBsAg loss rate at the end of the 16-week EYP001a treatment and at 24-week of follow-up (Week 40).
- To establish the Hepatitis B virus (HBV) virologic failure rate (breakthrough) during the 24-weeks follow-up period after stopping EYP001a with ongoing NA.
- To determine HBV viral response, HBV Pg/Precore Ribonucleic Acid (pgRNA), Hepatitis B core-related antigen (HBcrAg) and Hepatitis B Surface e-Antigen (HBeAg), Antibody to Hepatitis B e

antigen (Anti-HBe) and Antibody to Hepatitis B surface antigen (Anti-HBs) at the end of the 16-week EYP001a treatment and Week 40 of follow-up.

- To explore the safety profile of EYP001a treatment in combination with NA.
- To determine the plasma concentration of EYP001a and pharmacodynamic (PD) markers (plasma C4 (7 α -hydroxy-4-cholesten-3-one)), fibroblast growth factor (FGF) 19 and BAs.

2.3 Endpoints

2.3.1 Primary endpoint(s)

- Efficacy assessed as HBsAg decline ($\Delta \log_{10}$) from Day 1 to Week 16 of treatment.

2.3.2 Secondary endpoints(s)

Efficacy will be assessed as follows:

- HBsAg responder rate (decrease from baseline ≥ 1.0 on the \log_{10} scale) at Week 16 of treatment and Weeks 20, 28 and 40 of follow up.
- HBsAg responder rate (decrease from baseline ≥ 0.5 on the \log_{10} scale) at Weeks 12 and 16 of treatment and Weeks 20, 28 and 40 of follow up.
- HBsAg loss rate (% patients with HBsAg < Lower Limit of Quantification (LLOQ/TND) at Week 16 of treatment and Weeks 20, 28 and 40 of follow-up.
- HBsAg loss rate (% patients with HBsAg < Lower Limit of Quantification (LLOQ/TD) at Week 16 of treatment and Weeks 20, 28 and 40 of follow-up.
- HBsAg loss rate (Proportion of results that are Target Not Detected versus Target Detected) at Week 16 of treatment and Weeks 20, 28 and 40 of follow-up.
- Relapse rate HBsAg (% patients who became negative [HBsAg < LLOQ], then increased with HBsAg > LLOQ) at Week 16 of treatment period and Weeks 20, 28 and 40 during follow-up period.
- Virologic failure rate (breakthrough) of Hepatitis B virus Deoxyribonucleic Acid (HBV-DNA) (% patients with a confirmed quantifiable HBV DNA increase of $\geq 1\log_{10}$ HBV DNA copies/mL above LLOQ) assessed at Week 16 of treatment period and Weeks 20, 28 and 40 during follow-up period.
- % patients with HBV DNA < Lower Limit of Quantification (LLOQ/TND) at baseline, Week 4, 8, 12 and 16 of treatment and Weeks 20, 28 and 40 of follow-up
- % patients with HBV DNA < Lower Limit of Quantification (LLOQ/TD) at baseline, Week 4, 8, 12 and 16 of treatment and Weeks 20, 28 and 40 of follow-up
- HBV-pgRNA decline ($\Delta \log_{10}$) from Day 1 to Weeks 4, 8, 12, 16 of treatment period and Week 40 of maintenance period.
- HBcrAg decline ($\Delta \log_{10}$) from Day 1 to Weeks 4, 8, 12, 16 of treatment period and Week 40 of maintenance period.
- HBeAg quantification for HBeAg pos patients and changes at Week 16 of treatment and Week 40 of follow-up.
- Fibroscan Vibration Controlled Transient Elastography (VCTE) change from screening value to Weeks 16 and 40 or Early Termination (ET) value.

Safety and Tolerability will be assessed as:

- Treatment-emergent adverse events (TEAEs) (including Serious Adverse Event (SAEs))
- All-cause mortality

- Clinical laboratory tests
- Pruritus assessment (VAS and Q5D)
- Vital signs (blood pressure, heart rate, respiratory rate, and temperature)
- Concomitant medications
- Physical examinations
- 12-lead Electrocardiogram (ECG).

Pharmacokinetics (PK) assessed will be as:

- Plasma concentration of EYP001a or any relevant active metabolites (as identified in an ongoing phase 1 study).

PD biomarkers will be assessed as:

- Plasma C4 (7 α -hydroxy-4-cholesten-3-one)
- FGF19
- Plasma primary and secondary BAs.

2.4 Sample Size

The primary endpoint is HBsAg reduction. Improvement of 1.0 on a log₁₀ scale at 16 weeks is considered to be clinically meaningful. The expected accrual rate is 2 to 4 patients per week but does not affect the sample size calculation. Note that the accrual rate will not affect sample size calculations. All assumptions are given in Table 1.

Table 1 Assumptions for primary endpoint	
Primary Endpoint	HBsAg reduction vs baseline on a log ₁₀ scale (“Chg”)
Null hypothesis	H0: Chg _{exp} – Chg _{ctrl} = 0
Alternative hypothesis	Ha: Chg _{exp} - Chg _{ctrl} = -1.0
SD of change vs baseline in experimental arm	1.08
SD of change vs baseline in control arm	1.08
Drop-out	10% over total study duration
Randomization ratio	3:1 for experimental:control (i.e. nE/nC=3)
Power	80%
Type I error rate (1-sided)	0.05

Chg: Change vs baseline; Ctrl: Control arm; Exp: Experimental arm; H0: Null Hypothesis; Ha: Alternative Hypothesis; SD: Standard Deviation

Patients who have dropped out, will be assumed to have a zero-difference vs baseline for conservativeness. To take this into account, the assumed effect of -1.0 on a log₁₀ scale, will be multiplied by 0.9, resulting in an assumed effect of -0.9. Using these assumptions, based on a test, 49 patients will need to be enrolled. Calculations are based on a t-test.

Note that the final analysis will be done, using a general linear model for repeated measures. Using this type of model, a better power is expected, thus sample size calculations can be considered conservative.

To calculate the power to detect a difference in HBsAg loss rate, we assumed a proportion of 0.5% in the placebo arm, and of 10% in the experimental arm. A trial including 49 patients results in a power of about 55% for this endpoint (using an un-pooled estimate of the variance), using a one-sided α of 0.05.

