#### *11.3.3.2. Secondary Efficacy*

HBsAg responder rate (decrease from baseline  $\geq 1.0$  on the  $\log_{10}$  scale and decrease from baseline  $\geq 0.5$  on the  $\log_{10}$  scale) and HBsAg loss rate (proportion of HBsAg < LLOQ) at Week 16 of treatment and Week 20, Week 28 and Week 40 of follow-up will be analysed as key secondary endpoints at 16 weeks, and 40 weeks. Proportion of patients of Target not detected will be analysed as exploratory endpoint. HBsAg responder rate (decrease from baseline  $\geq 0.5$  on the  $\log_{10}$  scale) will also be analysed at Week 12 of treatment. At 16 and 40 weeks, these endpoints will be analysed taking into account multiplicity by a combination of a hierarchical fixed test procedure and a Hochberg procedure (See [Section 11.4.2](#)), using a this Pearson Chi-square test. At other timepoints, analyses for these two endpoints will be descriptive.

Relapse rate HBsAg (% patients who became negative [HBsAg < LLOQ], then increased with HBsAg > LLOQ) at Week 16 of treatment period and Weeks 20, 28 and 40 during the follow-up period will be summarized by frequency counts and percentages.

Virologic failure rate (breakthrough) of HBV DNA (% patients with a confirmed quantifiable HBV DNA increase of  $\geq 1\log_{10}$  HBV DNA copies/mL above LLOQ) assessed at Weeks 16 of treatment, 20, 28 and 40 during follow up period will be summarized by frequency counts and percentages.

HBV-pgRNA decline ( $\Delta \log_{10}$ ) and HBcrAg decline ( $\Delta \log_{10}$ ) from Day 1 to Weeks 4, 8, 12 and 16 of the treatment period and Week 40 of maintenance period, HBeAg quantification for HBeAg positive patients and changes at Week 16 of treatment and Week 40 of follow-up and Fibroscan VCTE change from screening value to the Weeks 16 and 40 or ET visit will be summarized through descriptive statistics.

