### 11.4.2. Testing strategy and power for key secondary endpoints

Multiplicity is taken into account by using a combination of a hierarchical fixed test procedure and a Hochberg procedure.

Only in case the primary endpoint is significant at 16 weeks, the key secondary endpoint “HBsAg loss rate” will be tested at the same one-sided  $\alpha$  level of 0.05, using a Hochberg procedure. This procedure goes as follows: the p-values will be ordered from small to large

$p_{(1)} \leq p_{(2)}$ . largest p-value  $p_{(2)}$  will be compared to  $\alpha=0.05$ . If significant, then both hypotheses will be rejected. If not, the smallest p-value is compared to  $\alpha/2=0.025$ . If significant, then only the hypothesis corresponding to the smallest p-value is rejected.

At 40 weeks, the key secondary endpoints HBsAg responder rate and HBsAg loss rate will be tested a one-sided  $\alpha$  level of 0.05, using a Hochberg procedure.

To calculate the power to detect a difference in HBsAg loss rate, we assumed a proportion of 0.5% in the placebo arm, and of 10% in the experimental arm. A trial including 49 patients results in a power of about 55% for this endpoint (using an un-pooled estimate of the variance), using a one-sided  $\alpha$  of 0.05.

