2.5 Randomization

Sequential screening numbers will be assigned to patients at the time of informed consent signing. As they are enrolled into the study and after eligibility on Day -3 at the earliest and prior to dosing on Day 1 at the latest, patients will be assigned to a unique randomization number which are randomly assigned to treatment according to the specified randomization scheme.

The randomization schedule will be computer-generated before the start of the study.

An Interactive Web Response System (IWRS) will be employed to manage patient and treatment assignments.

Patients will be randomized prior to study drug (EYP001a or placebo and NA) administration on Day 1 in the ratio of approximately 3:1 (37:12) into 2 arms:

- Experimental Arm: EYP001a 200 mg QD + NA daily (37 patients)
- Control Arm: Placebo + NA daily (12 patients)

The ratio will be controlled through block randomization.

Patients will also be stratified per HBeAg status, based on medical history HBeAg value or established during screening, to obtain a balanced randomization to both study arms.

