- HBsAg responder rate (decrease from baseline ≥ 0.5 on the \log_{10} scale) at 16 of treatment and Weeks 40 of follow up.
 - Hypothesis: H_0 : Treatment is not associated with endpoint
 H_A : Treatment is associated with endpoint
 - Time Points: Week 16 and Week40.
 - The Pearson Chi-squared test will be used to compare the differences in proportions between the treatment groups at Week 16 and Week 40. At Week 16 and Week 40, this endpoint will consider multiplicity considering multiplicity by a combination of a hierarchical fixed test procedure and a Hochberg procedure (see section 3.4 for more detail). The analysis will be based on a one-sided test at a 5% level of significance.
- HBsAg loss rate (% patients with HBsAg < Lower Limit of Quantification (LLOQ)/TND) at Week 16 of treatment and Week 40 of follow-up.
 - Hypothesis: H_0 : Treatment is not associated with endpoint
 H_A : Treatment is associated with endpoint
 - Time Points: Week 16 and Week40.
 - The Pearson Chi-squared test will be used to compare the differences in proportions between the treatment groups at Week 16, and Week 40. At Week 16 and Week 40, this endpoint will consider multiplicity by a combination of a hierarchical fixed test procedure and a Hochberg procedure (see section 3.4 for more detail). The analysis will be based on a one-sided test at a 5% level of significance.
- HBsAg loss rate (% patients with HBsAg < Lower Limit of Quantification (LLOQ)/TD) at Week 16 of treatment and Week 40 of follow-up.
 - Hypothesis: H_0 : Treatment is not associated with endpoint
 H_A : Treatment is associated with endpoint
 - Time Points: Week 16 and Week 40.

- The Pearson Chi-squared test will be used to compare the differences in proportions between the treatment groups at Week 16, and Week 40. At Week 16 and Week 40, this endpoint will consider multiplicity by a combination of a hierarchical fixed test procedure and a Hochberg procedure (see section 3.4 for more detail). The analysis will be based on a one-sided test at a 5% level of significance.

3.4 Multiple Comparisons and Multiplicity Adjustments.

For the analysis of secondary endpoints during the final analysis, multiplicity will be considered by using a combination of a hierarchical fixed test procedure and a Hochberg procedure.

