Only if the primary endpoint is significant at 16 weeks, the key secondary endpoints “HBsAg loss rate (<LLOQ/TND and <LLOQ/TD)” and “HBsAg responder rates (B and A see section 3.2)” will be tested at the same one-sided α level of 0.05, using a Hochberg procedure at Week 16. This procedure goes as follows: the p-values will be ordered from small to large $p(1) \leq p(2) \leq p(3) \leq p(4)$. The largest p-value $p(4)$ will then be compared to $\alpha=0.05$. If significant, then all hypotheses will be rejected. If not, the next largest p-value $p(3)$ is compared to $\alpha/2=0.025$. If significant, then these hypotheses corresponding to $p(1)$, $p(2)$ and $p(3)$ are rejected. If not, the next largest p-value $p(2)$ is compared to $\alpha/3=0.017$. If significant, then both hypotheses corresponding to $p(1)$ and $p(2)$ are rejected. If not, the smallest p-value is compared to $\alpha/4=0.0125$. If significant, then only the hypothesis corresponding to the smallest p-value is rejected.

At 40 weeks, the key secondary endpoints HBsAg responder rates (B and A) and HBsAg loss rate will be tested a one-sided α level of 0.05, using a Hochberg procedure.

To calculate the power to detect a difference in HBsAg loss rate, we assumed a proportion of 0.5% in the placebo arm, and of 10% in the experimental arm. A trial including 49 patients results in a power of about 55% for this endpoint (using an un-pooled estimate of the variance), using a one-sided α of 0.05.

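### The stated 55% power for HBsAg loss belongs to an un-pooled approximation; the planned one-sided Pearson chi-square has about 3% power at 37:12

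*SAP*

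**What the plan says.** SAP 2.4 gives the power for HBsAg loss: "A trial including 49 patients results in a power of about 55% for this endpoint (using an un-pooled estimate of the variance"). SAP 3.4 repeats the statement, and protocol 11.4.2 has the same: "A trial including 49 patients results in a power of about 55% for this endpoint". In all three places the basis is that "we assumed a proportion of 0.5% in the placebo arm, and of 10% in the experimental arm", with a one-sided alpha of 0.05. Allocation is "in the ratio of approximately 3:1 (37:12) into 2 arms" (SAP 2.5).

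The analysis is described separately. For the responder and loss endpoints SAP 3.3 plans the same test, worded for the first of them as "The Pearson Chi-squared test will be used to compare the differences in proportions between the treatment groups at Week 16 and Week 40", and adds "The analysis will be based on a one-sided test at a 5% level of significance". Protocol 11.3.3.2 also specifies a chi-square ("using a this Pearson Chi-square test"). SAP 3.3 does not say how the chi-square is made one-sided, and its alternative hypothesis is non-directional: "Treatment is associated with endpoint". Neither document gives the power of the chi-square test.

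**The concern.** The power was computed for one statistic and the analysis uses another. The Pearson chi-square standardises the difference by the pooled variance. With 3:1 allocation and almost no placebo events, the pooled and un-pooled standard errors differ greatly, and neither normal approximation is reliable. The 55% may therefore say little about the chance that the planned test succeeds.

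What is at stake is interpretation. HBsAg loss is part of how the protocol defines functional cure, and it is the only secondary endpoint given a power figure. A reader who believes 55% would give a non-significant result far more weight than it deserves. The sample size, the primary analysis and the futility rule do not depend on this figure.

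**Working it through.** **Inputs.** Loss rates of 10% and 0.5%, one-sided alpha 0.05 and N = 49 (SAP 2.4, SAP 3.4, protocol 11.4.2); 37:12 (SAP 2.5); Pearson chi-square, one-sided 5% (SAP 3.3). Expected losses: 37 × 0.10 = 3.7 on EYP001a and 12 × 0.005 = 0.06 on placebo.

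**1. The plan's own figure (un-pooled normal approximation).**
- SE = √(0.10 × 0.90/37 + 0.005 × 0.995/12) = 0.0534
- Power = Φ(0.095/SE − 1.645) = Φ(0.136) = 55.4%, so the stated figure reproduces.

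**2. The same kind of approximation with the pooled variance.**
- Pooled rate = (3.7 + 0.06)/49 = 0.0767
- Pooled SE = √(0.0767 × 0.9233 × (1/37 + 1/12)) = 0.0884
- Power = Φ((0.095 − 1.645 × 0.0884)/0.0534) = Φ(−0.945) = 17.2%

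**3. Exact power of the planned test.** I assume no continuity correction and rejection when the signed pooled z exceeds 1.645. This is the most favourable to the plan of the chi-square readings checked. Power is the sum of the binomial probabilities of all rejecting outcomes.

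At 37:12 with no placebo losses (probability 0.995¹² = 94.2%):
- 7/37 vs 0/12: z = 1.627, one-sided p = 0.052, not significant
- 8/37 vs 0/12: z = 1.761, one-sided p = 0.039, significant

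At least 8 losses are therefore needed, against 3.7 expected. P(X ≥ 8) for Bin(37, 0.10) is 2.74%, and 0.942 × 2.74% = 2.6%. With one placebo loss, at least 13 are needed, which adds almost nothing. A simulation of 400,000 trials also gave 2.6%.

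**4. Other splits of 49.**

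| Split | Losses needed if none on placebo | Exact power | Pooled normal |
|---|---|---|---|
| 34:15 | 6 | 11.0% | 25.6% |
| 35:14 | 6 | 12.3% | 22.9% |
| 36:13 | 7 | 5.9% | 20.1% |
| 37:12 | 8 | 2.6% | 17.2% |
| 38:11 | 8 | 3.0% | 14.3% |
| 39:10 | 9 | 1.3% | 11.5% |
| 40:9 | 10 | 0.5% | 8.7% |

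Exact power moves in steps because the cut-off is a whole number of losses.

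**5. Sensitivity.**
- Comparing the usual two-sided p-value with 0.05: 0.26% at 37:12, at most 1.6% over these splits.
- With a continuity correction (one-sided): 0.07% at 37:12, at most 0.59%.
- At the Hochberg thresholds 0.025 and 0.0125: 0.26% and 0.02% at 37:12.
- With 10% drop-out and visit-n denominators, as in the mock loss tables (44 analysed, splits assumed): 3.9% at 33:11, and 0.6% to 7.8% from 35:9 to 31:13.
- Exact power of 55% would need a true EYP001a loss rate of about 22% at 37:12, 20% at 36:13 or 17% at 35:14.
- SAP 15 records that enrolment was suspended after about 25 randomizations. Illustrative splits of 25: 0.2% at 19:6, 0.6% at 18:7, 2.1% at 17:8.

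**The case against.** The strongest reply is that the documents disclose the un-pooled basis, the number is right on that basis, and nothing depends on it. N = 49 comes from the primary endpoint. At Week 16, HBsAg loss is tested only if the primary is significant. The protocol calls the study exploratory, and 55% already signals an underpowered endpoint. All of this is true. It limits the consequence to interpretation, but disclosing the variance formula does not tell a reader that the planned test has about one-twentieth of the stated power.

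A second objection is that two effects are combined. Changing from un-pooled to pooled variance takes 55% to 17%; replacing the approximation with exact enumeration takes 17% to about 3%. That is a fair distinction, and both steps are shown above. If 7/37 vs 0/12 counted as significant, power would still be only about 7%. Neither step comes near 55%.

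Third, the 13% ceiling depends on the range of splits: 32:17 gives 19.5%. That stands, but such splits are far from the planned 3:1.

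Fourth, enrolment was suspended, so a 49-patient figure may seem overtaken. Yet the SAP that records the suspension still states 55% twice, and power at about 25 patients is lower still.

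One further point stands. The SAP tests two versions of loss (below LLOQ with target not detected, and with target detected), the protocol tests one, and the 10% and 0.5% rates are not assigned to either SAP version.

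**Conclusion.** The concern holds. The 55% is a correct value of the disclosed formula but not the power of the planned analysis. Under the sponsor's rates, the one-sided 5% Pearson chi-square has exact power of about 3% at 37:12 and below 13% for every split of 49 from 34:15 to 40:9. If the drug works exactly as assumed, the test misses in about 97% of trials at 37:12 and in at least 87% over that range. This assumes an uncorrected signed pooled z; the two-sided and continuity-corrected readings give less. Gatekeeping and the Hochberg thresholds can only keep or lower these figures. The point should be fixed because it misstates what a null result would mean, but it leaves the primary endpoint, the sample size and the futility rule untouched.

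**What to change.** In SAP 2.4, SAP 3.4 and protocol 11.4.2, replace the 55% statement with:

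> Under the assumed rates (10% vs 0.5%), the exact power of the planned one-sided 5% Pearson chi-square test (uncorrected, signed pooled z) is about 3% at 37:12, and below 13% for any split of 49 from 34:15 to 40:9, before gatekeeping and the Hochberg thresholds, which can only keep or lower it. A non-significant HBsAg loss result is therefore not evidence of no effect.

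Put no figure for about 25 patients in these planning sections. Once the analysed arm sizes are known, compute the exact power for them and report it in SAP 15 or the study report.

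Switching to an un-pooled (Wald) test is not a remedy. Its exact power at 37:12 would be 69%, but its type I error reaches 21% at a common loss rate of 10%.

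The cost is replacement wording in three places (the protocol change could go through a clarification letter, as already used in this study) and one recomputed figure. No test, sample size, Hochberg family or data collection changes. The downside is that the endpoint is openly shown to have almost no power.
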